[Part 3 of 7 of the document. The other parts are not shown.]

An AE is any untoward medical occurrence in a subject or clinical investigation subject administered an investigational product. An AE does not necessarily have a causal relationship with the medicinal product. For this study, the study drug is E2609.

The criteria for identifying AEs in this study are:

- Any unfavorable and unintended sign (including an abnormal laboratory finding), symptom, or disease temporally associated with the use of an investigational product,

whether or not considered related to the investigational product (Note: It is not necessary to report every sign or symptom as a separate AE if the overall disease [diagnosis] is being reported as an AE.)

- Any new disease or exacerbation of an existing disease
- Any deterioration in nonprotocol-required measurements of a laboratory value or other clinical test (eg, ECG or x-ray) that results in symptoms, a change in treatment, or discontinuation of study drug
- Recurrence of an intermittent medical condition (eg, headache) not present pretreatment (Baseline)
- An abnormal laboratory test result should be considered an AE if the identified laboratory abnormality leads to any type of intervention, discontinuation of study drug, or withholding of study drug, whether prescribed in the protocol or not

All AEs observed during the study will be reported on the eCRF. All AEs, regardless of relationship to study drug or procedure, should be collected beginning from the time the subject signs the study ICF through the last visit (Visit 20, as shown in [Table 7](#)). Subjects who fail screening primarily due to AE(s) must have the AE(s) leading to screen failure reported on the Screening Disposition eCRF. SAEs will be collected for 3 months after the last dose of study drug, ie, through to the final Follow-Up visit (Visit 20). However, any SAEs volunteered by subjects after this time point must be reported according to standard procedures. (revised per Amendments 04 and 05)

Abnormal laboratory values should not be listed as separate AEs if they are considered to be part of the clinical syndrome that is being reported as an AE. It is the responsibility of the investigator to review all laboratory findings in all subjects and determine if they constitute an AE. Medical and scientific judgment should be exercised in deciding whether an isolated laboratory abnormality should be classified as an AE. Any laboratory abnormality considered to constitute an AE should be reported on the Adverse Event eCRF.

Abnormal ECG (QTc) results, if not otherwise considered part of a clinical symptom that is being reported as an AE, should be considered an AE if the QTc interval is more than 450 ms and there is an increase of more than 60 ms from baseline. Any ECG abnormality that the investigator considers as an AE should be reported as such.

Cognitive decline will be assessed as a safety assessment in addition to an efficacy assessment. Cognitive assessments include the ADAS-cog₁₄, MMSE, ISLT and CBB (see [Section 9.5.1.3.1](#)). If these assessments show cognitive decline during the Treatment Period, and if this cognitive decline is considered by the investigator to be excessive relative to the subject's recent AD history, this finding should be reported as an AE.

AEs that might indicate signals of possible drug abuse potential will require a more detailed follow-up through completion of a specific eCRF form. This includes AEs that fall into the following categories and examples of such AEs are provided in [Appendix 4](#).

- Euphoric mood
- Elevated mood

- Feeling abnormal
- Feeling drunk
- Feeling of relaxation
- Thinking abnormal
- Hallucination
- Inappropriate affect
- Mood disorders and disturbances
- Drug tolerance
- Psychosis
- Dissociative state

It is the responsibility of the investigator to review the results of the C-SSRS in all subjects and determine if any result constitutes an AE. Medical and scientific judgment should be exercised in deciding whether an isolated suicidality rating scale response should be classified as an AE (see [Section 9.5.1.5.11](#) for a description of the C-SSRS).

The following AEs will require the collection of information sufficient to provide a detailed description of the event, treatment and outcome to the Medical Monitor for the study: any treatment-emergent significant laboratory abnormality; any seizures, herpes zoster infection, severe infection; any moderate to severe drug rash or any rash lasting more than 72 hours (regardless of severity); amyloid-related imaging abnormalities (vasogenic edema, macrohemorrhage, an area of superficial siderosis, or a new microhemorrhage); a “yes” answer to Type 4 or 5 suicidal ideation, or a “yes” response to any suicidal behavior on the C-SSRS.

All AEs must be followed through the final Follow-Up visit (Visit 20), or until resolution, whichever comes first. All SAEs must be followed to resolution or, if resolution is unlikely, to stabilization. (revised per Amendment 04)

Every effort must be made by the investigator to categorize each AE according to its severity and its relationship to the study treatment.

Assessing Severity of Adverse Events

AEs will be graded on a 3-point scale (mild, moderate, severe) and reported in the detail indicated on the eCRF. The definitions are as follows:

- | | |
|----------|--|
| Mild | Discomfort noticed, but no disruption of normal daily activity |
| Moderate | Discomfort sufficient to reduce or affect normal daily activity |
| Severe | Incapacitating, with inability to work or to perform normal daily activity |

The criteria for assessing severity are different than those used for seriousness (see [Section 9.5.1.5.2](#) for the definition of an SAE).

Assessing Relationship to Study Treatment

Items to be considered when assessing the relationship of an AE to the study treatment are:

- Temporal relationship of the onset of the event to the initiation of the study treatment
- The course of the event, especially the effect of discontinuation of study treatment or reintroduction of study treatment, as applicable
- Whether the event is known to be associated with the study treatment or with other similar treatments
- The presence of risk factors in the study subject known to increase the occurrence of the event
- The presence of nonstudy, treatment-related factors that are known to be associated with the occurrence of the event

Classification of Causality

The relationship of each AE to the study drug will be recorded on the eCRF in response to the following question:

Is there a reasonable possibility that the study drug caused the AE?

Yes (related) A causal relationship between the study drug and the AE is a reasonable possibility.

No (not related) A causal relationship between the study drug and the AE is not a reasonable possibility.

9.5.1.5.2 SERIOUS ADVERSE EVENTS AND EVENTS ASSOCIATED WITH SPECIAL SITUATIONS

An SAE is any untoward medical occurrence that at any dose:

- Results in death
- Is life-threatening (ie, the subject was at immediate risk of death from the AE as it occurred; this does not include an event that, had it occurred in a more severe form or was allowed to continue, might have caused death)
- Requires inpatient hospitalization or prolongation of existing hospitalization
- Results in persistent or significant disability/incapacity
- Is a congenital anomaly/birth defect (in the child of a subject who was exposed to the study drug)

Other important medical events that may not be immediately life-threatening or result in death or hospitalization but, when based on appropriate medical judgment, may jeopardize the subject or may require intervention to prevent one of the outcomes in the definition of SAE listed above should also be considered SAEs. Medical and scientific judgment should be exercised in deciding whether expedited reporting is appropriate in such situations.

For this study, the following events should always be considered serious and reportable using the criteria of important medical event if the event does not meet other serious criteria: new onset seizures, ocular herpes.

In addition to the above, events associated with special situations include pregnancy or exposure to study drug through breastfeeding; AEs associated with study drug overdose, misuse, abuse, or medication error. These events associated with special situations are to be captured using the SAE procedures but are to be considered as SAEs only if they meet one of the above criteria. All AEs associated with special situations are to be reported on the eCRF whether or not they meet the criteria for SAEs.

All SAEs must be followed to resolution or, if resolution is unlikely, to stabilization.

The following hospitalizations are not considered to be SAEs because there is no “AE” (ie, there is no untoward medical occurrence) associated with the hospitalization:

- Hospitalizations for respite care
- Planned hospitalizations required by the protocol
- Hospitalization planned before informed consent (where the condition requiring the hospitalization has not changed after study drug administration)
- Hospitalization for administration of study drug or insertion of access for administration of study drug
- Hospitalization for routine maintenance of a device (eg, battery replacement) that was in place before study entry

If possible, a blood sample for the measurement of study drug plasma concentration should be drawn at the first report of an SAE or a severe unexpected AE and at its resolution.

9.5.1.5.3 LABORATORY MEASUREMENTS

Clinical laboratory tests to be performed, including hematology, chemistry, urinalysis, and CSF are summarized in [Table 4](#). Subjects should be in a seated or supine position during blood collection. [Table 6](#) and [Table 7](#) show the visits and time points at which blood for clinical laboratory tests and urine for urinalysis will be collected in the study.

See [Section 9.3.3](#) for safety criteria for discontinuation from study drug related to absolute counts of CD4, CD8, and B lymphocytes, and for lymphocyte subset counts.

Table 4 Clinical Laboratory Tests

| Category | Parameters |
|-----------------------------|--|
| Hematology | Hematocrit, hemoglobin, platelets, red blood cell count, and white blood cell count with differential (bands, basophils, eosinophils, lymphocytes, monocytes, neutrophils). PT, PTT, and INR (Screening and Baseline only) (revised per Amendment 02) |
| Chemistry | |
| Electrolytes | Bicarbonate, calcium, chloride, phosphate, potassium, sodium |
| Liver function tests | Alanine aminotransferase, alkaline phosphatase, aspartate aminotransferase, gamma glutamyl transpeptidase, direct bilirubin, total bilirubin |
| Renal function tests | Blood urea/blood urea nitrogen, creatinine |
| Other | Albumin, cholesterol, globulin, glucose, lactate dehydrogenase, total protein, triglycerides, uric acid |
| Urinalysis | Bacteria, casts, crystals, epithelial cells, glucose, ketones, occult blood, pH, protein, red blood cells, specific gravity, white blood cells |
| Other | Lymphocyte T and B cell subset analyses (see Table 5). Regulatory T cells (revised per Amendment 04) PBMCs (revised per Amendment 02) Ig analyses (IgG, IgA, and IgM). Viral screen (HCVAb [Hepatitis C] and HbsAg [Hepatitis B]). Viral characterization (including HSV1, HSV2 and CMV, etc) Serum pregnancy test (females of child bearing potential only) Tuberculosis Interferon Gamma Release Assays Tests for thyroid function (thyroid stimulating hormone, free triiodothyronine and free thyroxine) and vitamin B12 Blood sample for storage for subsequent testing of immune status Cerebrospinal fluid sampling |

Whenever unscheduled lymphocyte subset tests are performed or whenever scheduled lymphocyte subsets are repeated, a CBC with differentials must also be repeated. (revised per Amendment 02)

CMV = cytomegalovirus, HBsAg = hepatitis B surface antigen, HCVAb = hepatitis C virus antibody, HSV = herpes simplex virus, Ig = immunoglobulin, INR = International Normalized Ratio, PBMC = peripheral blood mononuclear cell, PT = prothrombin time, PTT = partial thromboplastin time.

The 8 different surface markers (including but not limited to CD3, CD4, CD8, CD45, CD19, CD16, CD56, and CD14) and total lymphocyte counts will be measured in order to provide the lymphocyte subset data as shown in [Table 5](#). In addition, Regulatory T cells will be measured. Current sponsor data supports the literature showing there is an age-related decline in lymphocyte subsets (see [Appendix 5](#)). These data have been used to revise the LLNs for CD4 (T helper cells), CD8 (cytotoxic T cells), and CD19 (B cells) absolute counts to the population-adjusted LLNs of 396, 157, and 74 cells/ μ L, respectively) (revised per Amendments 02 and 04).

Table 5 Lymphocyte Subtypes Inclusive in BD Trucount™

| Cell Type | Cell Surface Markers |
|----------------------|----------------------|
| T lymphocytes | CD3 |
| T helper cells | CD3+, CD4 |
| Cytotoxic T cells | CD3+, CD8 |
| Mature B cells | CD3-, CD19 |
| Natural killer cells | CD3-, CD16, CD56 |
| Macrophages | CD14 |

(Table 5 revised per Amendment 04)

Clinical laboratory tests during all phases of the study will be performed by a central laboratory. All blood and urine samples will be collected and sent to the central laboratory on the day of collection unless otherwise instructed. In cases of a safety concern, blood samples will be split (or 2 samples drawn) to allow a local laboratory analysis in addition to the central laboratory. Laboratory certification as available will be included in the final clinical study report for this study.

A laboratory abnormality may meet the criteria to qualify as an AE as described in this protocol (see [Section 9.5.1.5.1](#) and the case report form [CRF] Completion Guidelines). In these instances, the AE corresponding to the laboratory abnormality will be recorded on the Adverse Event eCRF.

9.5.1.5.4 VITAL SIGNS AND WEIGHT MEASUREMENTS

Vital sign measurements (ie, systolic and diastolic BP [mmHg], heart rate [bpm], respiratory rate [per minute], body temperature [in centigrade], and weight [kg]) will be obtained at the visits designated in [Table 6](#) and [Table 7](#) by a validated method. Measurements of sitting BP and heart rate will be obtained. All BP measurements should be performed on the same arm, preferably by the same person.

9.5.1.5.5 PHYSICAL EXAMINATIONS

A complete physical examination will be performed at Screening as described in [Section 9.5.1.2.1](#). At Baseline and during the Randomization Phase, routine physical examinations will take place as shown in [Table 7](#). These examinations will include the cardiovascular system, respiratory system, and neurological system. Health status will be evaluated by brief evaluation of the eyes, ears, nose, throat, and other physical conditions of note. The subject must be queried regarding changes in physical status since the last examination. A urogenital examination will only be required in the presence of clinical symptoms related to this region. Documentation of the physical examination will be included in the source documentation at the site. Only changes from screening physical examination findings that meet the definition of an AE will be recorded on the Adverse Events eCRF.

9.5.1.5.6 ELECTROCARDIOGRAMS

Electrocardiograms will be obtained as designated in [Table 6](#) and [Table 7](#). Twelve-lead standard ECGs will be recorded in triplicate (1 minute apart) after subjects have been resting

in the supine position for at least 5 minutes.

On any study day when ECG, vital signs, and blood samples are taken, these procedures should be conducted in the following order: ECG first, followed by vital signs, and then blood samples.

An ECG abnormality may meet the criteria of an AE as described in this protocol (see [Section 9.5.1.5.1](#)) and the CRF Completion Guidelines. In these instances, the AE corresponding to the ECG abnormality will be recorded on the Adverse Events eCRF.

9.5.1.5.7 SAFETY MRI

Safety brain MRI assessments will be performed at the times shown in [Table 6](#) and [Table 7](#). Additional safety MRI scans can be performed at unscheduled visits if clinically necessary. MRI acquisition and interpretation will be organized centrally to ensure reproducibility and consistency between units involved.

Safety MRIs will be acquired using a standardized procedure that will include fluid-attenuated inversion recovery (FLAIR), gradient-echo, T1, and diffusion-weighted sequences to determine the presence of focal lesions including, but not limited to, evidence for ischemic and hemorrhagic stroke, subdural hematoma, neoplasm, arteriovenous malformation, micro and macrohemorrhages, superficial siderosis, lacunar infarcts, white matter abnormalities, and vasogenic edema. The imaging sequence for the Screening/safety MRI will include: T2 weighted anatomic MRI to rule out major white matter changes, cerebral infarction or other structural lesions, and a high-resolution 3D T1-weighted scan with isotropic voxels with volumes of 1 mm³ or less. In addition, both FLAIR for the detection of vasogenic edema and T2 Gradient Recall Echo for the detection of microhemorrhages will be acquired. The 3D dataset will be reconstructed in transverse slices in Digital Imaging and Communications in Medicine format. The results of this MRI assessment will also be used as the Baseline Period MRI, against which changes after drug administration will be compared. Further details of the MRI protocol can be found in the Imaging Acquisition Guideline. MRI acquisition and interpretation will be organized centrally to ensure reproducibility and consistency between units involved. MRI imaging will be conducted on separate days from the scheduled visits. MRI imaging should be conducted within the 7 days before Visits 14, 16, and 18 and at the final Follow-Up Visit (Visit 20). (revised per Amendment 04) In the event of an Unscheduled Visit, the investigator in consultation with the sponsor will determine whether or not a safety MRI should be conducted. If an ED Visit takes place, an MRI is to be conducted if not already performed during the preceding 90 days.

At any time during the treatment period, subjects will be discontinued from study drug if they develop any of the following features on MRI: vasogenic edema, macrohemorrhage, an area of superficial siderosis, or a symptomatic microhemorrhage. All of these features must be reported as study specific AEs (or AEs of special interest). These subjects will undergo an ED Visit within 7 days after discontinuation and 4 Follow-Up Visits at 2, 4, 8 and 12 weeks after the last dose of treatment. (revised per Amendment 04) Subjects will also undertake an

Unscheduled Visit (with MRI) at approximately 30 days after the visit at which such MRI features were first identified. Additional visits may be arranged if clinically indicated in the opinion of the investigator, and may occur later than 12 weeks after the final dose of study drug.

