Note: All screening and baseline assessments are to be completed within 50 days, plus an additional window of up to 30 days if required (revised per Amendment 02). The interval between availability of the results of the last screening assessment (PET scan) and the first baseline (Visit 2) assessments should be as short as possible and ideally should not exceed 7 days. Visit 3 (Randomization) (see [Table 7](#)) should occur no more than 10 days after completion of the Baseline visit (Visit 2) and confirmation of eligibility to continue in the study, unless additional time is required to take Exclusion Criterion No.20 into account (revised per Amendment 02). Thus, the total Prerandomization Phase may be up to 60 days, plus an additional window of up to 30 days if required (revised per Amendment 02).

- a: Subjects who initially consented to CSF collection and provided a baseline CSF sample but did not provide a postrandomization sample will be approached to consider re consenting to postrandomization CSF sample collection even if they are beyond Week 5 (Visit 7); however, subject re consent to this procedure is optional for these subjects. For those subjects who do consent to CSF sample collection: CSF will be collected by LP after fasting (preferred), or at least 2 hours after the most recent meal. A gravity drip collection method must be used. Subjects will be encouraged to stay at the site after completion of LP for medical observation. The timing of the Baseline LP needs to be scheduled carefully such that subsequent LPs (Visit 7 [or later postrandomization timepoint] and Visit 18) can be performed between 4 and 8 hours postdose and at a similar time of day (± 1 hour) for each individual subject. If the LP and cognitive tests are performed on the same day, the LP must be performed after the cognitive tests have been completed and the subject should rest and drink some fluid to hydrate before the LP. The CSF sample will be used for PK and PD assessments. A CSF sample will also be stored for testing in the event that the subject develops TEAEs that warrant further investigation (eg, treatment-emergent infection). (revised per Amendments 01, 02, and 04)

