| Randomization | X | | | | | | | | | | | | | | | | | | | | | | | | | | |
| Dispense study drug ^x | X | X | X | X | X | X | X | X | X | X | X | X | X | X | X | X | | | | | | | | | | | |

Footnotes for Table 7

ADAS-cog₁₄ = Alzheimer's Disease Assessment Scale - Cognitive subscale (14 items), CBB = CogState Brief Battery, CBP = childbearing potential, CDR = Clinical Dementia Rating scale, CSF = cerebrospinal fluid, C-SSRS = Columbia Suicide Severity Rating Scale, ECG = electrocardiogram, ED = Early Discontinuation, FAQ = Functional Assessment Questionnaire (also known as the Functional Activities Questionnaire), Ig = immunoglobulin, ISLT = International Shopping List Task, LP = lumbar puncture, MMSE = Mini Mental State Examination, MRI = magnetic resonance imaging, PBMC = peripheral blood mononuclear cell, PD = pharmacodynamics, PET = positron emission tomography, PK = pharmacokinetics, UNS = unscheduled, W2 = new Week 2 follow-up visit, W8 = new Week 8 follow-up visit. (revised per Amendment 04)

- a: Visit 3 should be conducted no more than 10 days after completion of the Baseline visit (Visit 2) assessments and confirmation of eligibility to continue in the study, unless additional time is required to take Exclusion Criterion #20 into account. (revised per Amendment 02) A window of ± 3 days will be permitted for Visit 4 to 14 inclusive. A window of ± 10 days will be permitted for Visit 15 to 18 inclusive. A window of ± 3 days will be permitted for the Follow-Up Visits. If use is made of the permitted visit windows, every effort should be made to bring the subject back in line with the "weeks elapsed since first dose" at subsequent visits.
- b: Subjects who discontinue taking study drug prematurely for any reason will undergo an ED Visit within 7 days of their last dose of study drug. In addition, Follow-Up Visits will be scheduled 2, 4, 8, and 12 weeks after the last dose of study drug (Visit W2, 19, W8, and Visit 20, respectively). (revised per Amendments 04 and 05)
- c: All subjects, regardless of whether they complete all 18 months of treatment or discontinue study drug prematurely, will complete 4 post-treatment Follow-Up visits; 2, 4, 8, and 12 weeks after the last dose of study drug (Visits W2, 19, W8, and 20, respectively). If clinically indicated, more frequent safety assessments can be made as UNS assessments or visits during the post-treatment Follow-Up period. (revised per Amendment 04)

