- q: Safety MRIs will be acquired using a standardized procedure that will include gradient echo, long tau inversion recovery, and diffusion-weighted imaging sequence images in MRI will be read by an approved central reader. MRI imaging will be conducted on separate days from the scheduled visits. MRI imaging should be conducted within the 7 days before Visits 14, 16, 18, and 20. In the event of an Unscheduled Visit, the investigator in consultation with the sponsor will determine whether or not a safety MRI should be conducted. If an ED Visit takes place, an MRI is to be conducted if not already performed during the preceding 90 days. A volumetric MRI sequence will be collected in all subjects immediately following all safety MRI assessments. (revised per Amendment 01)
- r: PET scanning will be performed with a locally approved amyloid β imaging agent, eg, Amyvid, if available or an agent under clinical investigation if no agents are approved locally; the imaging agent must remain unchanged for an individual subject throughout the study. A PET scan will only be performed at an ED Visit if the subject has been treated with study drug for at least 39 weeks. A PET scan will only be performed at Visit 18 or ED if the subject has a valid Screening PET scan for the purposes of longitudinal analyses; subjects who were determined to be eligible for the study on the basis of an historical PET scan will not have a PET scan performed at Visit 18 or ED (revised per Amendment 02)
- s: Site staff will contact the subject or the caregiver or informant the day before the PK blood sampling to provide instructions that subjects must not take their study drug at home on the day of the PK blood sampling. During this telephone contact with the subject or the caregiver or informant, the site staff should document the time that the subject took their study drug that day, ie, the day before the PK blood sampling.

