Complete blood counts and lymphocyte subset absolute counts and percentages will be measured (by a centralized laboratory) every week for the 1st month, every 2 weeks for the next 2 months (Months 2 and 3) and monthly for the next 3 months (Months 4, 5, and 6). Thereafter, they will be monitored every 3 months until the end of the Treatment Period and at all 4 Follow-Up Visits at 2, 4, 8, and 12 weeks after the last dose of study drug. Serum IgG, IgA, and IgM will be monitored monthly for the 1st 3 months, at 6, 12, and 18 months, and at the Follow-Up Visits that occur 4, 8, and 12 weeks after the last dose of study drug. (revised per Amendment 04)

Peripheral blood mononuclear cells (PBMCs) will be collected at Baseline, during treatment, and

post-treatment for exploratory immunomodulatory and immune-based analyses.

Centralized skin assessments, using standardized photography, will be conducted by a reviewing dermatologist at baseline and at 3-month intervals during the Treatment Period. These assessments will specifically include evaluation of any areas of depigmentation or rash. Subjects will also be questioned by the investigator at each visit to identify any changes that might represent a drug-induced rash/reaction or infection. Subjects and their caregivers/ informants will be instructed to contact the investigator if they see any lesions or other symptoms that might be associated with a drug-induced rash/reaction or infection, so such AEs can be reviewed promptly.

Baseline and on-study blood and DNA samples will be taken and stored for all subjects, and CSF samples will be taken and stored for all subjects from whom CSF samples were collected (revised per Amendments 02 and 04). These samples may be tested for exploratory biomarkers associated with study drug or disease, or in the event that a subject develops AEs that warrant further investigation (eg, to test if a subject with a treatment-emergent infection was exposed to any suspected infective agents before treatment with study drug).

Safety brain MRI assessments will be performed at Screening, at 6, 12, and 18 months during the Treatment Period and at the final Follow-Up Visit. Additional safety MRI scans are to be performed as clinically necessary. MRI acquisition and interpretation will be organized centrally to ensure reproducibility and consistency between units involved.

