9.1.1 Prerandomization Phase

The Prerandomization Phase includes a Screening Visit and a Baseline Visit. All Screening Visit assessments must be completed and eligibility to progress must be confirmed before any Baseline Visit assessments are performed. All Screening Visit and Baseline Visit assessments must be completed within 50 days (plus an additional window of up to 30 days if required [revised per Amendment 02]) and a window of no more than 10 days is to be observed between the completion of all Baseline Visit assessments (including confirmation of eligibility following all Baseline Visit assessments) and randomization into the study at Visit 3 (revised per Amendment 02). Thus, the Prerandomization Phase will last for up to 60 days, plus an additional window of 30 days if required (revised per Amendment 02). The series of assessments conducted during this phase will determine eligibility for randomization into the study.

Inclusion criteria are discussed in [Section 9.1](#) and detailed in [Section 9.3.1](#). Before randomization, the clinician will provide a judgment on the classification of a subject as either MCI/Prodromal or likely mild to moderate AD. (revised per Amendment 01) This judgment may be discussed and reviewed with the Sponsor or Sponsor's representative, as necessary.

Results of the Screening safety magnetic resonance imaging (MRI) will be valid for 90 days from the date of scanning. Results of the lumbar puncture (LP) from subjects who voluntarily consent for CSF measurement will be valid for 90 days from the date of testing. Results of Screening PET scans conducted specifically for this study and for use in the

longitudinal analyses will also be valid for 90 days from the date of scanning. These assessments will not need to be repeated should the subject be randomized within that time period either under their original subject identification number or under a new re-screening subject identification number. Historical PET scans used for determination of eligibility only (ie, not used for the longitudinal analyses) are valid for 12 months. (revised per Amendment 02)

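### The early-discontinuation MRI can be waived by any scan in the preceding 90 days, so read literally the pre-dose Screening MRI can replace it in early discontinuers

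*Protocol*

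**What the plan says.** Table 7 lists a safety and volumetric MRI at the ED Visit. Section 9.5.1.5.7 (Safety MRI) and Table 7 footnote q then make it conditional: "If an ED Visit takes place, an MRI is to be conducted if not already performed during the preceding 90 days". Neither place says which scans count.

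The Screening scan is one of the protocol's safety MRIs. The synopsis (Safety Assessments) says: "Safety brain MRI assessments will be performed at Screening, at 6, 12, and 18 months during the Treatment Period". Section 9.5.1.5.7 covers the times in both Table 6 and Table 7, and says of the Screening scan: "The results of this MRI assessment will also be used as the Baseline Period MRI, against which changes after drug administration will be compared". Section 9.1.1 lets it age before randomization: "Results of the Screening safety magnetic resonance imaging (MRI) will be valid for 90 days from the date of scanning", and "These assessments will not need to be repeated should the subject be randomized within that time period".

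For the scheduled scans after randomization, footnote q says: "MRI imaging should be conducted within the 7 days before Visits 14, 16, 18, and 20". Visit 14 is Day 183. Subjects who stop early "will undergo an ED Visit within 7 days of their last dose of study drug" (Table 7 footnote b) and have Visit 20 12 weeks after the last dose (footnote c).

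**The concern.** The waiver plainly aims to avoid repeating a recent scan. It works when the recent scan is an on-treatment one. Before the first on-treatment scan, however, the only routine MRI that can fall inside the 90-day look-back is the Screening MRI. That scan is the baseline, so it cannot show a change since dosing began. A site that applies the sentence as written could skip the ED scan on the strength of it.

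Safety is the primary objective, and early stopping is foreseeable: Section 9.3.3 requires discontinuation for, among other things, most rashes lasting more than 72 hours, herpes zoster, severe infection and any seizure. For such a subject the ED scan is the only scheduled MRI near the end of exposure. The ED rule for PET in the same table is tied to time on drug (at least 39 weeks), whereas the MRI rule has no such condition.

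**Working it through.** No sample size, alpha or power figure is involved. This is date arithmetic on the protocol's own windows.

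**Inputs**
- Look-back: 90 days before the ED Visit (Section 9.5.1.5.7; footnote q), taken as inclusive.
- g, days from Screening MRI to Day 1: at most 90 (Section 9.1.1). This agrees with the Table 6 note that "the total Prerandomization Phase may be up to 60 days, plus an additional window of up to 30 days if required", since 60 + 30 = 90. No expected or minimum gap is given, so the values below are assumptions.
- t, days from Day 1 to the ED Visit.
- Lag from last dose to ED Visit: 0 to 7 days (footnote b).
- Visit 20: 12 weeks, or 84 days, after the last dose (footnote c).

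**Condition for the waiver.** At the ED Visit the Screening MRI is g + t days old. It satisfies the literal rule while g + t ≤ 90, that is, t ≤ 90 − g.

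| Assumed gap g | Latest t with ED MRI waived | Study day |
|---|---|---|
| 14 | 90 − 14 = 76 | Day 77 |
| 30 | 90 − 30 = 60 | Day 61 |
| 45 | 90 − 45 = 45 | Day 46 |
| 60 | 90 − 60 = 30 | Day 31 |
| 90 | 90 − 90 = 0 | Day 1 (effectively none) |

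If the ED Visit comes 7 days after the last dose, the corresponding time on drug is 7 days shorter.

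**Both terms matter.**
- Same gap, different time: g = 30 and t = 30 gives 60 (waived); g = 30 and t = 70 gives 100 (scan required).
- Same time, different gap: g = 20 and t = 35 gives 55 (waived); g = 60 and t = 35 gives 95 (scan required).
- Order reversed between subjects: g = 30 and t = 60 gives 90 (waived); g = 60 and t = 31 gives 91 (scan required). The subject with about twice the time since first dose is the one not scanned.

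**Next scheduled scan.** Visit 20 is at last dose + 84 and the ED Visit at last dose + 0 to 7, so Visit 20 falls 84 − 7 = 77 to 84 days after the ED Visit, about 11 to 12 weeks. With g = 30 and ED on Day 61, Visit 20 is nominally Day 61 + 77 = 138 to Day 61 + 84 = 145. Footnote q allows the scan up to 7 days earlier, so from Day 131.

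**Comparison with continuing subjects.** Their first on-treatment scan is in the 7 days before Day 183, that is, Day 176 to 182. With a gap of at least 1 day, the latest waived ED Visit is Day 90, so Visit 20 is nominally no later than Day 90 + 84 = 174. These are nominal dates; the ±3-day visit windows can shift them slightly.

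**The case against.** The strongest reply is that the sentence has a sensible narrower reading. Footnote q belongs to the Randomization Phase table, while the Screening MRI sits in Table 6 under its own footnote. In both places the waiver follows directly on the list of scans around Visits 14, 16, 18 and 20, so a reader may take it to mean those scans. A baseline comparator is also an odd candidate for a follow-up scan. This reading is plausible, and many sites would probably adopt it, but the text does not state it. The Screening scan carries the same row label in Table 6 as the later scans do in Table 7, and Section 9.5.1.5.7 covers both tables.

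The second reply is that little is lost. This largely stands. Every affected subject is still due an MRI at Visit 20, nominally before a continuing subject's first routine scan. Unscheduled MRIs are allowed if clinically necessary, the ED Visit includes a neurological examination, and a subject stopped for an MRI finding has just been scanned. Safety MRI is summarised descriptively, and the volumetric endpoints are at 6, 12 and 18 months, so an ED scan this early feeds none of them.

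A reader might infer from the reversed pair above that the waiver turns on the screening gap and not on exposure. That is too strong: time since first dose is one of the two terms, and with the gap held fixed a longer time restores the scan. Nor do the documents support saying that these subjects have no post-dose MRI at all, or that they are watched less closely than the design's own schedule for continuing subjects.

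**Conclusion.** The point holds as a drafting fault in a stated rule. Read literally, the waiver lets the pre-dose baseline scan replace the ED MRI for ED Visits up to 90 minus the screening gap days after Day 1, and the cut-off moves with that gap. What is lost is the routine scan near the end of exposure in early discontinuers; the next scheduled scan is about 11 to 12 weeks later.

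The conclusion rests on the literal reading, on an inclusive 90-day count and on assumed gaps. The MRI comes before the PET scan, the Baseline Visit and up to 10 days to randomization, so gaps may be long and the waiver window short. With no discontinuation rate in the protocol, the number affected cannot be estimated and could be zero. No endpoint, error rate or power figure changes. Minor and optional.

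**What to change.** In Section 9.5.1.5.7 and Table 7 footnote q, keep the requirement for an MRI at the ED Visit and replace the waiver condition with: *unless one has been performed after the first dose of study drug and within the preceding 90 days*. The Screening MRI could then never satisfy the rule, whatever the gap, while a recent on-treatment or unscheduled post-dose scan still would.

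The cost is one phrase in two places. The downside is that a few briefly exposed subjects have an ED scan that the literal rule would have spared them; Table 7 already lists that scan.
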